3. GENERAL INFORMATION

Objective	To compare dry eye symptoms as well as corneal and conjunctival staining of Systane Complete Multi-Dose PF, versus the Walgreen's Lubricant Balance eye drop.		
	The hypothesis is that mild to moderate dry eye subjects will exhibit less frequent and severe dry eye symptoms after using Systane Complete Multi-Dose PF versus those who use Walgreen's Lubricant Balance.		
Test Article(s)	Systane Complete Multi-Dose PF Walgreen's Lubricant Balance		
Sample size	70 subjects		
Study Population	Subjects who currently have mild to moderate symptoms of dry eye.		
Number of sites	One		
Study Design	Single site, prospective, double-masked, randomized-controlled study with two arms		
Masking	Double-masked		
Variables	Primary: Dry eye symptom frequency and severity as measured by the SANDE questionnaire change after 2 weeks of QID use.		
	Exploratory:		
	 Comparing corneal and conjunctival staining before and after 2 weeks of QID use of their assigned drop. Comparing Non-invasive TBUT times of the subjects in the two arms of the study, before and after 2 weeks of QID use of their assigned drop. Dry eye symptom frequency and severity as measured by the SANDE questionnaire after 1 week of QID use. 		
Duration / Follow-up	Screening Visit to 2 weeks follow-up		

The study will be registered with clinicaltrials.gov.

The study will be conducted in compliance with the protocol, GCP and applicable regulatory requirements

5. INTRODUCTION

There are a vast array of lubricating eyedrops available on the market that can confuse and frustrate consumers. Many consumers view these the various products as "all the same" and often do not base their purchase on science or their doctor's recommendation, but a variety of other factors including cost, store merchandising, and a potential view that all products are the same.

However, even products that list the same active ingredient can have vastly different inactive ingredients resulting in a potentially different outcome for the patient. For example, Walgreen's Lubricant Balance eyedrop and Alcon's Systane Complete Multi-Dose Preservative Free (PF) eyedrop has the same active ingredient (0.6% propylene glycol), however, Walgreen's Lubricant Balance eyedrop is preserved in benzalkonium chloride (BAK), a known cause of ocular dryness and corneal and conjunctival staining.¹ To date, there is little data comparing the clinical outcomes between these two eyedrops.

The purpose of this study is to compare dry eye symptoms as well as corneal and conjunctival staining of Systane Complete Multi-Dose PF, versus the Walgreen's Lubricant Balance eye drop.

6. OBJECTIVE(S)

To compare dry eye symptoms as well as corneal and conjunctival staining of Systane Complete Multi-Dose PF, versus the Walgreen's Lubricant Balance eye drop.

7. SUBJECTS

7.1. Subject Population

Eligible test subjects will be 18-45 years of age who currently have mild to moderate symptoms of dry eye as defined by a screening SANDE score of 20 to 55 inclusive (equivalent to OSDI score of 12 to 32).²

A total of 70 subjects at one site will be enrolled. Both eyes of a subject must be enrolled. Subjects must meet the inclusion criteria. Prior to enrollment, subjects will be provided information on the study and asked to sign a patient information and consent form to participate. The patient information and consent form will be approved by an appropriate ethics committee.

7.2. Inclusion Criteria

Subjects are eligible for the study if they meet the following criteria:

Note: Ocular criteria must be met in both eyes.

- Subjects who currently have mild to moderate symptoms of dry eye as defined by a screening SANDE score of 20-55 inclusive (equivalent to OSDI score of 12 32).²
- Subjects between the ages of 18-65.

- Subjects willing to comply with the prescribed regimen and schedule of eye drops.
- Subjects willing to attend all study visits.
- Subjects willing to discontinue any current artificial tear use 24 hours prior to the baseline study visit.

7.3. Exclusion Criteria

v 1.0

If any of the following exclusion criteria are applicable to the subject or either eye, the subject should not be enrolled in the study.

- Ocular anterior segment infection, inflammation, abnormality, or active disease.
- History of herpetic keratitis or ocular surgery.
- Recent (within 1 year) thermal meibomian gland expression procedure including Lipiflow, iLux, or TearCare.
- Recent (within 1 year) blepharitis debridement procedure including BlephEx.
- Screening SANDE score > 55 (equivalent to OSDI score of >32).² This is indicative of a severe dry eye.
- Screening SANDE score < 20 (equivalent to OSDI score of <12).² This is indicative of a clinically normal eye.
- Screening non-invasive TBUT < 2 seconds, or > 10 seconds.³
- Screening NaFl score < 3 (clinically normal eye) or > 10 (severe dry eye).⁴
- Pregnant or lactating.
- Current use of contact lenses.
- Any change in eye drop regimen, whether OTC or RX in the last 90 days.

The principal investigator reserves the right to declare a patient ineligible or nonevaluable based on medical evidence that indicates they are unsuitable for the trial.

Pregnancy has a known effect on the stability of refractions and visual acuity. As such, subjects who become pregnant during the study will not be discontinued but their data may be excluded from analyses of effectiveness.

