8. STUDY DESIGN

8.1. Study Design

Single site, prospective, double-masked, randomized-controlled, two-arm study of the dry eye symptoms as well as corneal and conjunctival staining in subjects using 2 different eyedrops. Subjects will be assessed at a screening visit, and 2 follow-up visits. Clinical evaluations will include patient questionnaire, tear-breakup time, and slit lamp exam.

The primary outcome measure is Dry eye symptom frequency and severity as measured by the SANDE questionnaire change after 2 weeks of QID use.

Exploratory outcome measures are as follows:

- Comparing corneal and conjunctival staining before and after 2 weeks of QID use of their assigned drop.
- Comparing Non-invasive TBUT times of the subjects in the two arms of the study, before and after 2 weeks of QID use of their assigned drop.
- Dry eye symptom frequency and severity as measured by the SANDE questionnaire after 1 week of QID use.

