9.3. Study Methods and Measurements

All routine testing and basic eye examinations should be carried out at each study visit. Abnormalities should be recorded in the CRF "Comment" section. Specific study examination procedures are outlined below.

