10. ANALYSIS PLAN

10.1. Analysis Data Sets

All subjects who are enrolled in the study will be evaluated for safety. Efficacy analyses will be performed based on data from those eyes that complete the study.

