15. STANDARD EVALUATION PROCEDURES

Table 15.1. Proposed Visits and Study Assessments

(visits are by patient, with both eyes tested)

Activity	Recruit- ment	Follow-Up	Follow-Up
	Visit 1	Visit 2	Visit 3
Informed Consent	Х		
Demographics	Х		
General Information: Medical History	Х		
Non-Invasive Tear Breakup Time	Х		Х
Slit Lamp Exam and Staining Evaluation	Х		Х
SANDE Questionnaire	Х	Х	Х
Compliance Check		Х	Х
Monitor for Adverse Events		Х	Х
Complete Exit Form ¹			X

¹ Complete Exit Form upon termination of subject participation, or at Visit 3, whichever occurs first.

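### Section 7.3 permits discretionary exclusion of efficacy data after randomisation, with no requirement to decide before unmasking, and Section 10 does not close the gap

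*Combined protocol and SAP*

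**What the plan says.** Section 7.3 of the combined protocol and SAP contains two permissions.

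- **Pregnancy.** The section states that "subjects who become pregnant during the study will not be discontinued but their data may be excluded from analyses of effectiveness". Its justification is that "Pregnancy has a known effect on the stability of refractions and visual acuity". It gives no criterion, decision-maker or deadline for the exclusion.
- **Nonevaluable.** The principal investigator "reserves the right to declare a patient ineligible or nonevaluable based on medical evidence that indicates they are unsuitable for the trial". The condition is medical evidence of unsuitability. The sentence does not say whether the decision must come before randomisation, before Visit 3 or before unmasking.

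On what is measured, Section 8.1 says "Clinical evaluations will include patient questionnaire, tear-breakup time, and slit lamp exam". Section 9.2 and Table 15.1 list SANDE, non-invasive TBUT, slit lamp with staining, a compliance check and adverse events.

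On who is analysed, Section 10.1 says "Efficacy analyses will be performed based on data from those eyes that complete the study", and Section 18.1 treats attendance at the final visit as completion. Section 10.2 places the analysis on a per protocol population that is not defined anywhere.

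**The concern.** An exclusion that is optional, undated and made after randomisation can be decided once the subject's result is known. If the arm is also known, the comparison is no longer protected by randomisation.

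The pregnancy rule adds a second problem. Its stated ground has no bearing on SANDE, staining or TBUT, so the plan gives no reason for dropping those data. It also pulls against Section 10.1: a subject who becomes pregnant and attends Visit 3 is a completer and belongs in the efficacy set, yet 7.3 allows the data to be removed.

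At stake is the superiority claim on the primary endpoint, in a trial with 35 subjects per arm where a few removals can move the result.

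**Working it through.** **1. The plan's own figure.** Section 11 gives a difference of 7, SD 6, 90% power and 5% significance. By the two-sided normal formula, n per group = 2 × SD² × (1.960 + 1.282)² / difference² = 2 × 36 × 10.51 / 49 = 15.4, rounded up to 16, or 32 in total. This matches the stated figure. The noncentral t gives 16.5, so 17 per group. At 35 per arm, t-test power is about 99.8%, and 17 evaluable subjects per arm would still give about 91%. Loss of power is therefore not the issue; bias is.

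**2. Does the pregnancy rationale fit?** Set the ground in 7.3 (refraction, acuity) beside the assessments in 8.1, 9.2 and Table 15.1. Neither measure appears. Section 9.3 says "All routine testing and basic eye examinations should be carried out at each study visit", which might include acuity in practice but makes it neither an endpoint nor a listed assessment.

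**3. Does Section 10 prevent the exclusion?** Section 10.1 would keep a completer, 7.3 allows removal, and 10.2 leaves the per protocol set undefined. Section 8.2, on minimising bias, describes no masked data review and no point at which exclusions are fixed. No analysis of all randomised subjects is planned as a check.

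**4. Size when outcome and arm are both known.** Inputs: 35 per arm and SD 6 (Section 11), two-sample t-test (10.2), alpha 0.05 (10.3, taken as two-sided because that reproduces the sample size). Assumptions: normal SANDE changes with higher being worse, no true difference, and k removals, because the documents give no rate. Over 100,000 simulated trials, the k worst values were dropped from one arm:

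| k removed from one arm | False superiority for that arm | Two-sided error | Shift in difference (SANDE points) |
|---|---|---|---|
| 0 | 2.5% | 5.0% | 0 |
| 1 | 4.9% | 6.3% | −0.37 |
| 2 | 7.8% | 8.7% | −0.69 |
| 3 | 11.4% | 12.0% | −0.98 |

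**5. Size when exclusion ignores outcome.** Dropping 1, 2 or 3 subjects at random from one arm leaves false superiority at about 2.5% and the two-sided error at about 5.0%.

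**6. Size when outcome is known but arm is not.** With no true difference, dropping the worst 1, 2, 3 or 6 values regardless of arm leaves the one-direction error at 2.5% to 2.6% and the two-sided error at 4.9% to 5.1%. The arms are exchangeable, so the removals fall evenly on average. When a true difference exists, the poor results come more often from the worse arm. For an assumed true difference of 4, dropping the worst three lowers the estimated difference from 4.0 to about 3.4.

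**The case against.** The strongest reply is that the trial is double-masked. The figures in step 4 need knowledge of the arm, which masking withholds, and step 6 shows that knowing outcomes alone does not inflate false superiority. This stands while the mask holds. It does not dispose of the point, because nothing requires exclusions to be settled before the mask is broken.

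Second, the nonevaluable clause is conditional on medical evidence of unsuitability, and a poor symptom score is not obviously such evidence. This also stands: the discretion is not unlimited.

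Third, a reader might infer that both clauses remove data from subjects who stay on the drop and complete Visit 3. Only the pregnancy sentence says the subject is not discontinued. A subject declared nonevaluable could instead be discontinued under Section 9.5 and so fall outside the completer set anyway.

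Fourth, pregnancy is excluded at entry and the last visit is at Day 14 ± 2, so the pregnancy rule will affect very few subjects. The scenarios with k of 1 to 3 cannot realistically come from that rule alone. Of the two clauses, the nonevaluable one matters more.

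Finally, deleting wording in 7.3 alone would not secure the data, because the undefined per protocol set leaves the same room. This is correct, and the fix must reach Section 10.

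**Conclusion.** The point holds as a flaw in stated rules. Section 7.3 permits discretionary exclusion of efficacy data after randomisation, for pregnancy on a ground unrelated to the endpoints, and Section 10 does not prevent it. The change should be made.

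The rise in false superiority from 2.5% to about 5% to 11% is a worst case. It rests on an assumed one to three removals, all from one arm, made with knowledge of both outcome and arm. Truly masked exclusions do not inflate type I error; their cost is some precision, plus attenuation of a real difference if poor outcomes are the ones removed.

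A reader might go further and infer that the plan intends outcome-driven removal, or that the investigator's sight of SANDE scores is enough to produce false wins. The documents support neither. They leave post-outcome exclusion open without inviting it, and false superiority rises only if the arm is known too.

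**What to change.** - **Section 7.3, investigator's discretion:** limit the eligibility decision to the time before randomisation and delete the word nonevaluable.
- **Section 7.3, pregnancy:** delete the provision for excluding data and its refraction and acuity rationale. This concerns data handling only; clinical management of these subjects is unchanged.
- **Sections 10.1 and 10.2:** state that SANDE, staining and TBUT data of every randomised subject who has them are kept in the primary analysis. Confine any exclusion to a sensitivity analysis, decided and documented before unmasking, with reasons listed by arm. Define the per protocol set under the same rule if it is retained.

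The cost is rewording in 7.3 and a short addition to Section 10. No new data, visits or procedures are needed.

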8. STUDY DESIGN

8.1. Study Design

Single site, prospective, double-masked, randomized-controlled, two-arm study of the dry eye symptoms as well as corneal and conjunctival staining in subjects using 2 different eyedrops. Subjects will be assessed at a screening visit, and 2 follow-up visits. Clinical evaluations will include patient questionnaire, tear-breakup time, and slit lamp exam.

The primary outcome measure is Dry eye symptom frequency and severity as measured by the SANDE questionnaire change after 2 weeks of QID use.

Exploratory outcome measures are as follows:

- Comparing corneal and conjunctival staining before and after 2 weeks of QID use of their assigned drop.
- Comparing Non-invasive TBUT times of the subjects in the two arms of the study, before and after 2 weeks of QID use of their assigned drop.
- Dry eye symptom frequency and severity as measured by the SANDE questionnaire after 1 week of QID use.

8.2. Methods Used to Minimize Bias

Patient selection will be based on the patient's interest and the optometrist's opinion as to whether they are a suitable candidate for eyedrops. Subjects will be randomized to treatment groups.

All data collection will be completed through provided Case Report Forms (CRFs) or computer files generated by automated test equipment. All site personnel involved in the study will be trained in regard to conducting study-specific procedures.

8.3. Method of Assigning Subjects to Treatment Arms

Subjects will be assigned to Systane Complete Multi-Dose PF or the Walgreen's Lubricant Balance treatment groups in a 1:1 ratio using the method of randomly permuted blocks.

9. STUDY PROCEDURE

9.1. Informed Consent / Subject enrollment

No subject will be enrolled into the study who does not meet the inclusion/exclusion criteria and does not sign the current approved informed consent document. Informed consent will be obtained prior to collecting any data for the study. The original signed documents will be maintained by the investigator as a permanent part of the subject's medical records. A signed copy will be provided to the subject.

9.2. Visits and Examinations

Subjects will participate in 3 study visits. Visits will include an uptake visit and 2 follow up visits (Visit numbers 1-3 below). The visit schedule, complete with window and associated CRF forms, are displayed in Table 9.2-1. Details of each study visit, including testing to be conducted, are provided below.

Table 9.2-1. Visit Schedule

Visit Number	Visit Name	Visit Window	CRF Number
1	Recruitment	Day 0	1
2	Follow-Up Visit 1	Day 7 \pm 1 day	2
3	Follow-Up Visit 2	Day 14 \pm 2 days	3

9.2.1. Recruitment

At the recruitment visit, subjects will be consented, qualified for the study (compared with inclusion/exclusion criteria), and assigned a study ID/subject number. Subject numbers will be assigned sequentially at each site in the order of enrollment.

A medical history will be taken and exams will include the tests described below:

- slit lamp exam including evaluation of staining,
- non-invasive tear breakup time,
- SANDE questionnaire.

In addition, all site-specific, routine, usual standard of care measures should be undertaken.

Measurements should be made as described in section 9.3 below.

9.2.2. Follow-Up Visit 1

Exams will include the tests described below:

- SANDE questionnaire,
- compliance check.

In addition, all site-specific, routine, usual standard of care measures should be undertaken.

Any adverse events/serious adverse events (AEs/ SAEs) occurring during surgery will be noted at this visit. Any other problems during surgery and comments regarding surgery will be documented.

9.2.3. Follow-Up Visit 2

Exams will include the tests described below:

- slit lamp exam including evaluation of staining,
- non-invasive tear breakup time,

- SANDE questionnaire,
- compliance check.

In addition, all site-specific, routine, usual standard of care measures should be undertaken.

Any adverse events/serious adverse events (AEs/ SAEs) occurring during surgery will be noted at this visit. Any other problems during surgery and comments regarding surgery will be documented.

9.2.4. Exit Procedures

In the event of premature exit from the study, all study related examinations should be completed where possible. The Exit CRF should be completed, noting that the subject did not complete the study and the reason for premature study exit. If no premature exit from the study occurs, the Exit CRF should be completed at the end of Visit 3.

9.3. Study Methods and Measurements

All routine testing and basic eye examinations should be carried out at each study visit. Abnormalities should be recorded in the CRF "Comment" section. Specific study examination procedures are outlined below.

9.3.1. Non-Invasive Tear Breakup Time

Non-invasive TBUT determined using the Topcon CA-800. Subject will be instructed to blink 3 times and then hold eye open without blinking while test is being performed. Three (3) consecutive readings will be taken, and the average will be recorded in seconds. The Topcon CA-800 measuring is not able to be customized via software settings so the factory setting will be used. Both eyes will be tested, but for the purposes of this study only a single, randomly selected eye will be used for statistical analysis.

9.3.2. Staining

Baseline corneal and conjunctival staining with sodium fluorescein and Wratten filter assessed OU using the Academy of Ophthalmology 5 quadrant scheme. Each quadrant will be graded (0-3) giving a total score of 0-15 per eye. Again, both eyes will be evaluated, but only the total score of the single, previously selected eye in the TBUT measurement will be used for statistical analysis.

9.3.3 Questionnaires

The SANDE questionnaire, will be administered to subjects at all visits. The administrator should ensure the subjects understand the nature of the questions but should not interpret them for the subject.

v 1.0

9.4. Unscheduled Visits

Unscheduled exams may be conducted at the discretion of the Investigator with all relevant information from the exam recorded in the source documents and on the Unscheduled Visit pages within the CRF booklet.

9.5. Discontinued Subjects

Discontinued subjects are those who do not have an exit visit or who come into the office to be exited prior to the scheduled final study visit. Subjects may be discontinued from the study at any time if, in the opinion of the investigator, their continued participation in the study poses a risk to their health. The reasons for discontinuation include:

- a. Adverse event;
- b. Lost to follow-up;
- c. Subject decision unrelated to an adverse event;
- d. Protocol violation;
- e. Treatment failure;
- f. Other.

To ensure the safety of all subjects who discontinue prior to Visit 3, investigators should assess each subject and, if necessary, advise them of any therapies and/or medical procedures that might be needed to maintain their health. Any changes in medical health and/or use of concomitant medications should also be captured.

10. ANALYSIS PLAN

10.1. Analysis Data Sets

All subjects who are enrolled in the study will be evaluated for safety. Efficacy analyses will be performed based on data from those eyes that complete the study.

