10.2. Statistical Methodology

Analysis will be done on the per protocol population. For monocular outcomes, analysis will be performed on the study eye that was determined by randomization.

Superiority of Systane COMPLETE relative to Walgreens will be established if the mean SANDE score is significantly lower in the Systane COMPLETE group vs. Walgreens group.

Demographics, baseline characteristics, efficacy endpoints, and adverse events will be summarized descriptively. Summaries of these variables will include sample size, as well as the mean, median, standard deviation, minimum and maximum.

Primary Endpoint: Dry eye symptom frequency and severity as measured by the SANDE questionnaire change after 2 weeks of QID use (subject level). Total scores will be compared using a two-sample t-test.

The step-down methodology will be used on the other endpoints in the following order:

- Comparing corneal and conjunctival staining in the study eye before and after 2 weeks of QID use of their assigned drop (eye level). The corneal and conjunctival staining scores will be totaled from the 5 evaluation zones for analysis. Total scores will be compared using a two-sample ttest.
- Comparing Non-invasive TBUT times of the study eye in the two arms of the study, before and after 2 weeks of QID use of their assigned drop (eye level). Time will be compared using a two-sample t-test.
- Dry eye symptom frequency and severity as measured by the SANDE questionnaire after 1 week of QID use (subject level). Total scores will be compared using a two-sample t-test.

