11. SAMPLE SIZE JUSTIFICATION

Assuming a difference in means between groups of 7 (SANDE) and a pooled standard deviation of 6, the study would require a sample size of 16 subjects for each group (total sample size of 32 subjects) to achieve a power of 90% and a level significance of 5%. To increase the study power and account for dropout, the sample size is being increased to 70 subjects (35 in each arm) to thoroughly characterize the performance of the drops.

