18.2. Patient Discontinuation

Each study patient may voluntarily discontinue the study at any time they choose. Study patients who cannot complete the study for administrative reasons (e.g., non-compliance, failure to meet visit schedule, etc.) will be discontinued from the study. Study patients discontinued during the enrollment phase (prior to surgery) of the study will be replaced.

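### Superiority would rest on completers or an undefined per-protocol set, with no all-randomised efficacy analysis and no missing-data rule

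*Combined protocol and SAP*

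**What the plan says.** Two sentences define who enters the efficacy analysis, and they differ. Section 10.1 states: "Efficacy analyses will be performed based on data from those eyes that complete the study". Section 10.2 states: "Analysis will be done on the per protocol population". No section defines that population. The superiority criterion follows directly in Section 10.2: "Superiority of Systane COMPLETE relative to Walgreens will be established if the mean SANDE score is significantly lower in the Systane COMPLETE group". The test is a two-sample t-test. The only set that includes everyone enrolled is the safety set.

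Section 11 raises the sample from 32 to 70 partly to allow for dropout, but gives no rate. Sections 10 and 11 contain no imputation rule, no model for incomplete data and no sensitivity analysis.

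Several routes lead out of the efficacy set after randomisation. Section 9.5 lists adverse event, protocol violation and "Treatment failure" among the reasons for discontinuation. Section 18.2 adds non-compliance and missed visits. Section 7.3 lets the investigator "declare a patient ineligible or nonevaluable based on medical evidence that indicates they are unsuitable for the trial", and allows data from subjects who become pregnant to be left out of effectiveness analyses.

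On data collection, Section 9.3.3 says: "The SANDE questionnaire, will be administered to subjects at all visits". Section 9.2.4 asks for the study examinations at premature exit where possible.

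**The concern.** Randomisation makes the arms comparable only for the subjects who were randomised. Treatment failure, adverse events and non-compliance can all depend on how well the assigned drop works. If poor responders leave one arm more than the other, the completer means differ even when the drops do not. The bias favours Systane if its arm loses poor responders, and works against it if the comparator arm does. The protocol's Introduction gives a reason to expect the second: it holds the comparator's preservative to be a cause of dryness and staining.

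The set also cannot be built reproducibly. Compliance is checked at Visits 2 and 3, but no threshold links it to per-protocol status, and nothing says the set is fixed before unmasking. Section 18.1 ties completion to Visit 3, while Section 18.3 counts terminated subjects as having completed and Section 18.5 treats the two groups separately. That is a smaller wording point, but it bears on who is a completer.

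A subject who leaves after Visit 2 has a week-1 SANDE score that the primary test ignores. With no analysis that includes leavers, a reader could not tell whether a superiority result depends on who left.

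**Working it through.** **1. The plan's own figure.** Inputs from Section 11: difference 7, SD 6, power 90%, level 5% (sidedness is not stated; two-sided assumed). Normal formula: n per arm = 2(1.960 + 1.282)² × 6² / 7² = 15.4, rounded up to 16, or 32 in total. This matches the plan; a t-based calculation gives 17 per arm.

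**2. Power is not at stake.** At 35 per arm, power is 99.8%. With assumed losses of 10%, 20% or 30% (32, 28 or 24 completers per arm) it is 99.6%, 99.0% or 97.7%.

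**3. Upper bound on the bias.** Assume no true difference, and that exactly the worst scorers leave the Systane arm while nobody leaves the comparator arm. Losing 2, 4 or 7 of 35 shifts the completer difference by 0.7, 1.25 or 2.04 points in favour of Systane. With full data, significance needs a difference of 1.995 × 6 × √(2/35) = 2.86 points. False superiority becomes 7.8%, 15.5% or 31.6%, against a nominal 2.5%.

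**4. Exit only partly related to outcome.** Let exit be correlated 0.6 with the week-2 outcome. The bias should then be about 0.6 times the bound: 0.6 × 0.7 = 0.42, 0.6 × 1.25 = 0.75 and 0.6 × 2.04 = 1.22. Simulation (40,000 trials per setting, 35 per arm, SD 6, no true difference, two-sided 0.05) gives:

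| Poor responders lost from one arm only | Bias, points | False superiority, Systane loses | False superiority, comparator loses |
|---|---|---|---|
| 0 | 0 | 2.5% | 2.5% |
| 1 | 0.2 | 3.7% | 1.7% |
| 2 | 0.4 | 5.0% | 1.3% |
| 4 | 0.8 | 7.8% | 0.7% |
| 7 | 1.2 | 13.1% | 0.3% |

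Losing 4 from each arm gives 3.0%; losing 4 from Systane and 2 from the comparator gives 4.5%. For Systane losses of 4 or 7, a correlation of 0.3 gives 4.5% or 6.0%, and 0.8 gives 11% or 21%. Repeat runs of the main settings differed by at most 0.4 percentage points.

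**5. When the 7-point difference is real.** If the comparator loses 4 or 7 poor responders, the estimate shrinks to about 6.2 or 5.8. Power is still 98.9% or 96.9%.

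**6. Does modelling week 1 help?** Assume no true difference, Systane losses of 4 or 7, and a week-1/week-2 correlation of 0.7. Baseline was not in the simulated model.

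- Exit driven by the observed week-1 score: completers give 5.7% or 8.3%; a likelihood model on both weeks gives 2.6% or 2.5%.
- Exit driven by the week-2 outcome: completers give 7.8% or 13.1%; the model gives 4.7% or 6.8% (6.1% or 9.7% if the week-1/week-2 correlation is 0.5).
- Same mechanism, with missing week-2 scores made 3 points worse: 2.8% or 2.9%; 4 points worse: 2.5% or 2.2%.

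The model removes bias that the observed scores explain, and only part of the rest.

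**The case against.** The two descriptions of the set may nearly coincide. Completion is Visit 3, and subjects who are non-compliant or miss visits are discontinued, so completers and per-protocol subjects could be almost the same people. That is a fair reading. It softens the conflict between Sections 10.1 and 10.2, but supplies neither a definition nor an analysis of everyone randomised.

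The nonevaluable clause stands among the exclusion criteria, and its use after randomisation is possible rather than stated. Pregnancy can affect very few subjects in two weeks. Neither carries much weight.

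The larger error rates need one-sided loss and a fairly strong link with outcome in a masked two-week study. Milder cases are small: 2 Systane losses against 1 comparator loss give about 3.7%, and 7 against 7 about 3.0%. On the plan's own premise about the preservative, loss may fall on the comparator, which makes the completer test conservative for a superiority claim. All of this stands, and it limits the expected size. It does not remove the gap: if few subjects leave, the all-randomised analysis costs almost nothing and confirms the result; if many leave, it is needed.

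Two limits of the remedy also stand. Subjects who leave often have no week-2 score, so their contribution is modelled rather than observed. The model alone does not cure exit driven by the unseen outcome, and the delta that restored the nominal rate is specific to the simulated mechanism.

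**Conclusion.** The concern holds. As written, the superiority claim rests on completers or on an undefined per-protocol set, with no all-randomised analysis and no missing-data rule, in a trial that expects dropout and allows outcome-related exit. This is a risk of bias, not demonstrated bias.

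In the illustrations at correlation 0.6, the false-superiority rate runs from 0.3% to 13.1% around a nominal 2.5%, and bias reaches 1.2 SANDE points. Balanced losses leave little effect. These figures rest on assumed loss counts and exit correlations, because the plan gives neither; only the SD of 6 and the 35 per arm come from the plan. At the plan's inputs the harm would be a biased estimate or a false claim, not lost power. It should be corrected before unmasking.

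**What to change.** - Make all randomised subjects, analysed as assigned, the primary efficacy set. Do not apply the nonevaluable or pregnancy exclusions to it.
- Pre-specify a repeated-measures model of week-1 and week-2 SANDE with baseline SANDE as covariate and the week-2 contrast as primary.
- State how exit SANDE scores are used and how subjects with no score after baseline are handled. One option assigns exit scores only within the Section 9.2 windows (Day 7 ±1, Day 14 ±2). It would leave scores from Days 9 to 11 unassigned, so the choice should be deliberate.
- Add a delta-adjusted imputation that makes missing week-2 scores worse by 0 to 7 points (7 being the plan's design difference), and report the value at which the conclusion changes. Report losses by arm and reason.
- Define a per-protocol or completer set, fix it before unmasking, and report it as supportive.
- Reconcile Sections 10.1 and 10.2 on the analysis set, and Sections 18.1 and 18.3 on who has completed.

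The cost is SAP wording and somewhat more analysis work; no visit or measurement is added. The estimate may be diluted. If a fraction d of the Systane arm gained nothing over the comparator, the difference would be 7(1 − d) and the SD √(36 + 0.5 × 49 × d(1 − d)). For d = 20% these are 5.6 and 6.32, and power at 35 per arm is 95.5%. At 10% it is 98.8%, and at 30% it is 88.3%. The sensitivity analysis is part of the change, because the model corrects only losses that observed data explain.
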